## 8.5. Adverse Events and Serious Adverse Events

### 8.5.1. Evaluation of Adverse Events and Serious Adverse Events

For this protocol, an **adverse event (AE)** is any untoward medical occurrence (e.g., sign, symptom, disease, syndrome, intercurrent illness, clinically significant abnormal laboratory finding, injury or accident) that emerges or worsens following administration of investigational product and until the end of study participation that may not necessarily have a causal relationship to the administration of the investigational product. An AE can therefore be any unfavorable and/or unintended sign (including a clinically significant abnormal laboratory result), symptom, or disease temporally associated with the use of an investigational product, if considered related to the investigational product. A treatment-emergent AE is one that occurs after any period of exposure to treatment.

Pre-existing conditions, which increase in frequency or severity or a change in nature as a consequence of an investigational product use will also be considered an adverse event.

An unexpected AE is an adverse reaction, the nature or severity of which is not consistent with the applicable product information (e.g., Investigator's Brochure for an unapproved investigational product or package insert/summary of product characteristics for an approved product).

Any change in the study safety evaluations, (e.g., vital signs, injection site [REDACTED] [REDACTED]) after GL and FHL treatment determined to be clinically significant by the investigator must be reported as an AE.

A **serious adverse event (SAE)** is any untoward medical occurrence that results in any of the following outcomes:

- Death
- Life-threatening, (i.e., the subject was, in the opinion of the investigator, at immediate risk of death from the event as it occurred. It does not apply to an AE that hypothetically might have caused death if it were more severe)
- Persistent or significant disability/incapacity or substantial disruption of the subject's ability to carry out normal life functions
  - Requires in-patient hospitalization or prolongs hospitalization (i.e., a prolonged hospitalization beyond the expected length of stay;

**NOTE:** Hospitalizations for **elective medical/surgical procedures**, scheduled treatments, or routine check-ups are **not SAEs** by this criterion)

- Congenital anomaly/birth defect (i.e., an adverse outcome in a child or fetus of a subject exposed to the molecule or investigational product before conception or during pregnancy)
- Does not meet any of the above serious criteria but based upon appropriate medical judgement may jeopardize the subject or may require medical or surgical intervention to prevent one of the outcomes listed above (i.e., is a significant or important medical event)

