### 3. Objectives and Endpoints

[figure not shown]
All efficacy endpoints will be assessed using the last available assessment prior to GL treatment on Day 1 as baseline. All efficacy endpoints for FHL severity assessments, wherever applicable, will also be analyzed for GL severity assessments.

Objectives	Endpoints
Primary	

• To evaluate the efficacy and safety of DAXI for injection in the treatment of dynamic FHL

	

• Proportion of subjects achieving a score of 0 or 1 (none or mild) in FHL severity at maximum eyebrow elevation at 4 weeks after FHL treatment (Week 6) on the Investigator Global Assessment Forehead Wrinkle Severity (IGA-FHWS) scale

• Incidence, severity, and relationship to study drug of treatment-emergent AEs (TEAEs) and serious adverse events (SAEs) during the overall study duration.

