### **8.5.7. Investigational Product Causality and Severity**

Relationship of an AE to investigational product will be assessed as follows:

- **Definite:** There is a clinically plausible time sequence between the onset of the AE and the administration of investigational product; when the event responds to withdrawal of investigational product and/or recurs with re-administration of investigational product
- **Probable:** There is a clinically plausible time sequence between the onset of the AE and the administration of investigational product; the AE is unlikely to be caused by the concurrent/underlying illness, other drugs or procedures
- **Possible:** There may or may not be a clinically plausible time sequence between the onset of the AE and the administration of investigational product and a cause cannot be ruled out
- **Unrelated:** There is not a temporal or causal relationship to investigational product administration

The investigator is responsible for evaluating all AEs and determining the severity of the event. Severity will be categorized as mild, moderate to severe according to the following definitions:

- **Mild:** Event may be noticeable to subject; does not influence daily activities; usually does not require intervention
- **Moderate:** Event may be of sufficient severity to make subject uncomfortable; performance of daily activities may be influenced; intervention may be needed
- **Severe:** Event may cause severe discomfort; usually interferes with daily activities; subject may not be able to continue in the study; treatment or other intervention usually needed

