## **2.2.2 Safety Endpoints**

The primary safety endpoint is the incidence, severity, and relationship to study drug of TEAEs and SAEs during the overall study duration.

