## 3.3 Safety Assessments

### 3.3.1 Adverse Events

All adverse events (AEs) will be recorded and classified on the basis of MedDRA terminology. AE severity will be graded as mild, moderate, or severe as defined in Section 9.3.2 of the protocol. Relationship of an AE will be graded as definite, probable, possible, or unrelated. AEs with an onset on or after the date and time of trial treatment or events which were present before treatment and which worsened after treatment will be considered as treatment-emergent.

AEs with missing severity will be considered as “severe”. AEs with missing relationship will be considered as “related”. If the start of an AE relative to the administration of trial treatment cannot be definitively determined, it will be considered to have occurred after treatment and the event considered as treatment-emergent.

[REDACTED]

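### Protocol 8.5.1 contradicts itself on whether an adverse event must be considered related to the product; probably a drafting slip, but it should be corrected

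*Protocol*

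**What the plan says.** Protocol 8.5.1 opens by defining an AE as an untoward occurrence that is new or worse after dosing and "that may not necessarily have a causal relationship to the administration of the investigational product". The following sentence, presented as a conclusion from the first, says an AE can be any unfavorable or unintended sign, symptom or disease "temporally associated with the use of an investigational product, if considered related to the investigational product". The next paragraph says that a pre-existing condition which becomes more frequent, more severe or different in nature "as a consequence of an investigational product use will also be considered an adverse event".

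The SAE definition in the same section has no such condition: an SAE "is any untoward medical occurrence that results in any of the following outcomes".

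Protocol 8.5.7 grades causality on four levels. The lowest, Unrelated, reads "There is not a temporal or causal relationship to investigational product administration". SAP 3.3.1 uses the same scale: "Relationship of an AE will be graded as definite, probable, possible, or unrelated".

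The safety part of the primary objective in Protocol 3 is "Incidence, severity, and relationship to study drug of treatment-emergent AEs (TEAEs) and serious adverse events (SAEs) during the overall study duration", and SAP 2.2.2 repeats it. SAP 3.3.1 and 5.8 define treatment-emergence by onset or worsening after treatment, with no test of causality.

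**The concern.** Section 8.5.1 tells a site what to enter on the AE page of the eCRF. One sentence tells it to ignore causality, and the next can be read as making causality a condition of entry. Sites that resolve this differently would collect different sets of events for the same endpoint.

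The loss would occur at recording, before any analysis rule applies. The endpoint is the incidence of all TEAEs, not only related ones. The study is open-label and has no control group, so the investigator who judges relatedness knows the dose.

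**Working it through.** The documents give no expected AE rate and no power calculation for safety, so there is no figure to reproduce and no arithmetic to run. The check sets the passages side by side.

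1. **The two defining sentences (Protocol 8.5.1).** The first excludes causality as a requirement. The second claims to follow from it but ends with a causal condition. That condition does not follow from the first sentence and conflicts with it.

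2. **Pre-existing conditions.** The first sentence of 8.5.1 already covers worsening after dosing, without regard to cause. The pre-existing-conditions sentence ties the change to product use. SAP 3.3.1 and 5.8 go back to timing alone. The causal condition therefore appears twice in 8.5.1 and not at all in the SAP rule.

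3. **What the rest of the plan expects.** An Unrelated level in Protocol 8.5.7 and SAP 3.3.1 has a use only if unrelated events are entered. SAP 6.6.3 reports subjects with any AE separately from subjects with a related AE, which again assumes both kinds are in the database.

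4. **Does another rule override the phrase?** Protocol 8.5.2 requires all AEs to be collected and every subject-reported AE to be recorded. That rule uses the term AE, so it takes its scope from 8.5.1 and cannot repair it. Three rules do stand apart from relatedness: a positive item on the injection site evaluation (8.4.4, Table 9), clinically significant vital-sign findings (8.4.2), and clinically significant changes in the safety evaluations (end of 8.5.1). SAEs are also outside the condition.

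5. **One event followed through the literal reading.** Suppose a subject reports a non-serious event and the investigator judges it unrelated.
   - Under sentence two it is not an AE, so it is not entered.
   - The SAP's treatment-emergence rule works on recorded AEs, so the event cannot become a TEAE.
   - The SAP's rule that a missing relationship counts as related does not help. It applies to a recorded event with an empty field, not to an event that was never recorded.

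6. **Which results move, and which way.** Under this reading everything the site considers related is still entered, so the count of subjects with a related TEAE is unchanged. The counts for any TEAE and for unrelated TEAEs can only fall. Subjects are counted once within a system organ class or preferred term (Protocol 9.3.2, SAP 6.6.3). An omitted event therefore lowers a subject count only where that subject has no other recorded event in the same category.

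7. **Size.** This would need the rate of events judged unrelated, the share of sites that read the text literally, and the overlap of events within subjects. The documents give none of these.

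**The case against.** The best reply is that the intent is plain. The first sentence is the formal definition. The second says what an AE can be, which may be only an illustration. Protocol 8.5.2 prescribes a non-leading question to avoid bias in eliciting AEs. Section 8.5.5 singles out study-related AEs for extended follow-up, which presupposes that other AEs were recorded. Section 8.5.6 states a causality filter openly for new SAEs after the last contact, so the protocol can write such a filter as a rule when it wants one. Many sites would probably record unrelated events anyway.

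Most of this stands, and it limits how serious the point is. It does not remove the contradiction: the protocol nowhere says that the second sentence is illustrative, and nothing cancels its condition. A multicenter study should not rely on every site resolving the conflict the same way.

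Four stronger readings are tempting and are not supported:

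- *That the shortfall can be quantified.* A reader might assume a share of unrelated events, or a number of lost subjects, and express it as a fraction of a 15-subject cohort. Any such figure would be the assumption restated.
- *That the phrase makes the Unrelated category meaningless.* The inference runs more naturally the other way: the category shows a site that unrelated events belong in the record.
- *That a single injecting investigator controls what is recorded.* Injections are given by the principal investigator, but the study runs at 4 sites.
- *That dose escalation is compromised.* The review committee also sees photographs and videos, and its criteria are in a charter outside these documents. The events at risk are those judged unrelated to the product, and SAEs are not affected.

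**Conclusion.** The contradiction is real and stands in the current text. It is an internal inconsistency that should be fixed, not a flaw in the trial's design and not a reason to doubt the plan as a whole. If a site applies the condition literally, TEAE incidence in the primary safety endpoint is understated, mainly through non-serious, subject-reported events judged unrelated. The direction follows from the wording; the amount cannot be estimated from the documents.

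This rests on two assumptions: that at least one site follows the second sentence or the pre-existing-conditions sentence as written, and that such a site treats as related everything it would grade above Unrelated. Nothing in the documents shows that any site did so.

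**What to change.** Make three small changes:

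1. In the second sentence of Protocol 8.5.1, replace the closing condition with *whether or not considered related to the investigational product*.
2. Reword the pre-existing-conditions sentence so that worsening after treatment counts without attribution to the product, as in SAP 3.3.1 and 5.8.
3. Send sites a short memo confirming that events judged unrelated are entered on the AE page and graded Unrelated.

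The cost is a line or two of protocol text and one memo. Sample size, visits, causality scale and planned safety tables are unaffected, and the SAP needs no change. The correction has to reach sites while they are still recording, because no later analysis step can recover an event that was never entered.

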### **8.5.2. Assessment and Reporting Requirements**

The investigator will assess subjects after GL and FHL treatment and at each subsequent study visit for the occurrence of AEs. To avoid bias in eliciting AEs, subjects should be asked the following non-leading question: "How have you felt since your last visit?" All AEs (serious and non-serious) will be collected from signing of the ICF until the Final Evaluation Visit at each visit. Any AE reported by the subject must be recorded on the source documents and eCRFs.

All AEs will be collected from Day 1 until Week 38 or Final Evaluation Visit at the time points specified in the SOA (Section 1.3).

Medical occurrences that begin before the start of study intervention but after obtaining informed consent will be recorded on the Medical History/Current Medical Conditions section of the eCRF not the AE section.

All SAEs will be recorded and reported to Revance or designee immediately within 24 hours of their awareness of the event. All fatal or life-threatening SAEs should be telephoned to Revance or the designee's authorized representative as soon as the investigator learns of the event.

### **8.5.3. Serious Adverse Events**

[figure not shown]
The investigator must report an SAE to Revance or the designee's authorized representative within 24 hours of their awareness of the event:

1. Complete and return the SAE Form with all information known to date; including the investigator's assessment of causality
2. Contact Revance or the authorized representative for a fatal or life-threatening event as soon as the investigator or study staff are aware of the event
3. Obtain and maintain all pertinent medical records (discharge summary, autopsy report, etc.) and medical judgments of medical personnel who assisted in subject's treatment and follow-up
4. Provide follow-up information to Revance or the authorized representative within 24 hours of awareness

Regulatory Authorities, IRBs/ IECs, and investigators will be notified of SAEs in accordance with applicable regulations and requirements (e.g., ICH-GCP Guidelines, national regulations and local requirements).

[REDACTED]

[REDACTED]

### **8.5.5. Follow-up of Non-Serious Adverse Events**

Any AEs that are identified from Day 1 through the last scheduled study visit (or Final Evaluation Visit) must be recorded on the AE eCRF as ongoing.

Any clinically significant abnormal test results, (e.g., laboratory findings), at the final assessment should be followed to resolution or until determined by the investigator to be stabilized. Repeat tests may be indicated to establish this.

If a subject has any clinically significant, study-related AEs at the end of the study, the Medical Monitor should be notified, and every effort made by the investigator to arrange follow-up evaluations at appropriate intervals to document the course of the abnormalities until the medical monitor determines that follow-up is sufficient.

### **8.5.6. Follow-up of Post-Study Serious Adverse Events**

SAEs that are identified on the last scheduled contact (or Final Evaluation Visit) must be recorded on the AE eCRF and reported to Revance or designee according to the reporting procedures outlined in Section 8.5.2. This may include unresolved previously reported SAEs, or new SAEs. The investigator should follow these SAEs until the events are resolved, follow-up is sufficient, or the subject is lost to follow-up. The investigator should continue to report any significant follow-up information to the Medical Monitor, Revance or designee, and the IRB/IEC

up to the point the event has been resolved. Resolution means the subject has returned to the baseline state of health, or the investigator does not expect any further improvement or worsening of the subject's condition.

Any new SAEs reported by the subject to the investigator that occur after the last scheduled contact and are determined by the investigator to be reasonably associated with the administration of investigational product should be reported to Revance or designee and the IRB/IEC.

### **8.5.7. Investigational Product Causality and Severity**

Relationship of an AE to investigational product will be assessed as follows:

- **Definite:** There is a clinically plausible time sequence between the onset of the AE and the administration of investigational product; when the event responds to withdrawal of investigational product and/or recurs with re-administration of investigational product
- **Probable:** There is a clinically plausible time sequence between the onset of the AE and the administration of investigational product; the AE is unlikely to be caused by the concurrent/underlying illness, other drugs or procedures
- **Possible:** There may or may not be a clinically plausible time sequence between the onset of the AE and the administration of investigational product and a cause cannot be ruled out
- **Unrelated:** There is not a temporal or causal relationship to investigational product administration

The investigator is responsible for evaluating all AEs and determining the severity of the event. Severity will be categorized as mild, moderate to severe according to the following definitions:

- **Mild:** Event may be noticeable to subject; does not influence daily activities; usually does not require intervention
- **Moderate:** Event may be of sufficient severity to make subject uncomfortable; performance of daily activities may be influenced; intervention may be needed
- **Severe:** Event may cause severe discomfort; usually interferes with daily activities; subject may not be able to continue in the study; treatment or other intervention usually needed

## 9. Statistical Considerations

### 9.1. Sample Size Determination

The sample size is not determined by the power of any hypothesis testing. [REDACTED]

[REDACTED]

[REDACTED]

[REDACTED]

[REDACTED]

[REDACTED]

### 9.2. Populations for Analyses

For purposes of analysis, the following populations are defined and the summary groups for analysis will be based on the actual dose for FHL received (which is expected to be consistent with the enrollment cohorts):

Population	Description
Enrolled	All subjects who receive the GL treatment
GL-Evaluable	All enrolled subjects who have any post-GL treatment assessment of IGA-FWS at maximum frown
FHL-Evaluable	All enrolled subjects who receive the FHL treatment and have any post-FHL treatment assessment of IGA-FHWS at maximum eyebrow elevation
Safety	All enrolled subjects
Safety-FHL	All enrolled subjects who receive the FHL treatment

### 9.3. Statistical Analyses

The statistical analysis plan will be developed and finalized before database lock and will describe the detailed methods of analysis, the subject populations to be included in the analyses, and procedures for accounting for missing, unused, and spurious data. This section is a summary of the planned statistical analyses of the primary and secondary endpoints.

In general, descriptive summaries will include means, standard deviations, and ranges for continuous variables; and counts and proportions for categorical measures. Unless otherwise stated, a 95% CI will be provided for means and proportions. No formal hypothesis tests are planned, but may be performed as exploratory analyses. No multiplicity adjustments or imputation of missing data are planned.

### **9.3.1. Efficacy Analyses**

Unless otherwise noted, baseline for all efficacy assessments for GL refers to the last available assessment prior to GL treatment for those associated with GL severity and for FHL refers to the last available assessment prior to FHL treatment for those associated with FHL severity.

The primary efficacy endpoint will be the proportion of subjects achieving a score of 0 or 1 (none or mild) on the FHWS as assessed by IGA-FHWS at maximum eyebrow elevation at Week 6. The dose response in the proportion of responders at 4 weeks after the FHL treatment (Week 6) will be explored using the logistic regression stratified by baseline FHWS severity (last assessment prior to GL treatment at Day 1 Visit) and study center to assess the dose-response. Additional measures to assess the effectiveness outcomes will include the IGA-FHWS, PFHWS, GAIS evaluated at maximum contraction (eyebrow elevation) and at rest at each visit. Various responder endpoints associated with the FHWS, such as achieving certain status or certain magnitude of improvement from baseline, will be derived from these effectiveness outcomes for each visit. These responder endpoints will be analyzed by statistical models similar to that for the primary endpoint.

Duration of response will be evaluated by various time-to-event endpoints. Kaplan-Meier curves will be plotted by dose group for each time-to-event endpoint and median duration with associated 95% CIs will be provided.

Similar responder and time-event endpoints associated with the GL wrinkle severity defined based on the assessments for GL wrinkle severity such as IGA-FWS, PFWS or GAIS on GL, will be summarized similarly to those endpoints associated with FHWS. Efficacy outcomes will be summarized. Descriptive statistics will be provided for all efficacy variables at all timepoints. Note that exploratory analyses of the change in FHL severity from Day 1 (post-GL treatment) to Week 2 and from pre-FHL treatment (Week 2 pre-treatment) to post treatment will also be performed.

